### **3.2. Secondary Endpoint(s)**

#### **For AD:**

- *Proportion of participants achieving IGA score of clear (0) or almost clear (1) (on a 5-point scale) and a reduction from baseline of  $\geq 2$  points at Week 6 and other study visit time points specified in the SoA.*
- *Proportion of participants achieving EASI 75 (75% improvement from baseline) at study visit time points specified in the SoA.*
- *Proportion of participants having  $\geq 4$  points of reduction in weekly averages of Peak Pruritus Numerical Rating Scale (PP-NRS) from baseline at study visit time points specified in the SoA.*
- *Change from baseline in EASI total score at study visit time points specified in the SoA.*
- *Proportion of participants achieving IGA score of clear (0) or almost clear (1) at study visit time points specified in the SoA.*
- *Percent change from baseline in affected Body Surface Area (BSA) at study visit time points specified in the SoA.*
- *Incidence of treatment emergent adverse events (AEs) and serious adverse events (SAEs), clinically significant changes in vital signs, electrocardiogram (ECG), and laboratory tests.*
- *Incidence of severity grades in skin tolerability at times indicated in SoA.*

#### **For Psoriasis:**

- *Proportion of participants with PGA score clear (0) or almost clear (1) (on a 5-point scale) and  $\geq 2$  points improvement from baseline at Week 6 and other study visit time points specified in the SoA.*
- *Proportion of participants achieving PASI 75 (75% or greater improvement from baseline) at study visit time points specified in the SoA.*

- *Proportion of participants who achieved a Psoriasis Symptoms Inventory (PSI) score of 0 (not at all) or 1 (mild) on every item at study visit time points specified in the SoA.*
- *Change from baseline in PASI scores at study visit time points specified in the SoA (except Week 6).*
- *Percent change from baseline in PASI scores at study visit time points specified in the SoA.*
- *Proportion of participants with PGA score clear (0) or almost clear (1) and  $\geq 2$  points improvement from baseline at time points specified in the SoA.*
- *Percent change from baseline in BSA at study visit time points specified in the SoA.*
- *Incidence of treatment emergent adverse events (AEs) and serious adverse events (SAEs), clinically significant changes in vital signs, electrocardiogram (ECG), and laboratory tests.*
- *Incidence of severity grades in skin tolerability at times indicated in SoA.*

CCI

CCI

### 3.4. Baseline Variables

In general, for all analyses, baseline will be defined based on observations collected prior to first dose. Baseline values for demographics and height will be based on measures collected at Visit 1/Screening visit. Study Day 1 is defined as the day the subject receives first dose of study drug. For purposes of all other analyses including analyses for change from baseline, the baseline value will be defined as the last measurement before first dose on Day 1. If a value is missing on Day 1, then the last available observation

before Day 1 will be used. For the PP-NRS score, baseline will be defined as the average of all values recorded between Day -7 and Day -1.

### **3.5. Safety Endpoints**

Safety will be assessed by the spontaneous reporting of AEs, physical examinations, and clinical laboratory results in all subjects who receive at least one dose of the investigational product. Unscheduled safety assessments may be performed at any time during the study to assess any perceived safety concerns. Endpoints will be assessed as:

- Incidence of treatment emergent adverse events.
- Incidence of SAEs and AEs leading to discontinuation.
- Incidence of clinical abnormalities and change from baseline in selected clinical laboratory values, ECG measurements, and vital signs.

The safety endpoints will be defined in accordance with Clinical Data Interchange Standards Consortium (CDISC) and Pfizer Standards (CaPS).

#### **3.5.1. Adverse Events**

An adverse event will be considered a Treatment-Emergent Adverse Event (TEAE) if the event started during the effective duration of treatment. All events that start on or after the first dosing day and time/start time, if collected, but before the last dose plus the lag time will be flagged as TEAEs. The algorithm will not consider any events that started prior to the first dose date.

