4. STUDY DESIGN

4.1. Overall Design

This is a phase 2a, randomized, double blind, vehicle controlled, parallel group, multicenter study on the efficacy, safety, tolerability and PK of PF-07038124 0.01% QD versus vehicle control in the treatment of adult participants with mild to moderate AD or mild to moderate plaque psoriasis. In this study the efficacy of PF-07038124 ointment versus vehicle will be assessed in two different indications – there is a separate vehicle control group for each indication.

A total of approximately 88 participants with AD or psoriasis will be randomly assigned to study intervention in this basket trial design.

For AD, a maximum of approximately 56 participants will be randomly assigned to study intervention such that approximately 42 evaluable participants complete the study. Assuming a 25% drop out rate, approximately 28 participants will be randomized to either PF-07038124 or vehicle control to achieve approximately 21 completers in each group. Randomization will be stratified by baseline disease severity (mild [Investigator's Global Assessment or IGA = 2] vs. moderate [IGA = 3]). Up to 25% of AD participants will have an IGA score of 2 at baseline.

For psoriasis, a maximum of approximately 32 participants will be randomly assigned to study intervention such that approximately 24 evaluable participants complete the study. Assuming a 25% drop out rate, approximately 16 participants will be randomized to PF-07038124 or vehicle control to achieve 12 completers in each group. Randomization will be stratified by baseline disease severity (mild [Physician Global Assessment or PGA = 2] vs. moderate [PGA = 3]). Up to 25% of participants will have a PGA score of 2 at baseline.

The total duration of study participation will be approximately 17 weeks, including a screening period of up to 6 weeks, a double-blind, placebo-controlled treatment period of 6 weeks, and a safety follow-up period of 4-5 weeks from last dose of study drug to last study visit. The study intervention arms and duration for AD and psoriasis participants are the same (See [Section 1.1](#) for detailed Study Intervention Groups and [Section 1.2](#) for Study Schema).

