8.3.1. Time Period and Frequency for Collecting AE and SAE Information

The time period for actively eliciting and collecting AEs and SAEs (“active collection period”) for each participant begins from the time the participant provides informed consent, which is obtained before the participant’s participation in the study (ie, before undergoing any study-related procedure and/or receiving study intervention), through and including a minimum of 28 calendar days, except as indicated below after the last administration of the study intervention or until study completion or withdrawal, whichever is longer.

Follow-up by the investigator continues throughout and after the active collection period and until the AE or SAE or its sequelae resolve or stabilize at a level acceptable to the investigator and Pfizer concurs with that assessment.

For participants who are screen failures, the active collection period ends when screen failure status is determined.

If the participant withdraws from the study and also withdraws consent for the collection of future information, the active collection period ends when consent is withdrawn.

If a participant definitively discontinues or temporarily discontinues study intervention because of an AE or SAE, the AE or SAE must be recorded on the CRF and the SAE reported using the CT SAE Report Form.

Investigators are not obligated to actively seek AEs or SAEs after the participant has concluded study participation. However, if the investigator learns of any SAE, including a death, at any time after a participant has completed the study, and he/she considers the event to be reasonably related to the study intervention, the investigator must promptly report the SAE to Pfizer using the CT SAE Report Form.

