10.3.1. Definition of AE

AE Definition

• An AE is any untoward medical occurrence in a patient or clinical study participant, temporally associated with the use of study intervention, whether or not considered related to the study intervention.• NOTE: An AE can therefore be any unfavorable and unintended sign (including an abnormal laboratory finding), symptom, or disease (new or exacerbated) temporally associated with the use of study intervention.

Events Meeting the AE Definition

• Any abnormal laboratory test results (hematology, clinical chemistry, or urinalysis) or other safety assessments (eg, ECG, radiological scans, vital sign measurements), including those that worsen from baseline, considered clinically significant in the medical and scientific judgment of the investigator. Any abnormal laboratory test results that meet any of the conditions below must be recorded as an AE:
• Is associated with accompanying symptoms.• Requires additional diagnostic testing or medical/surgical intervention.• Leads to a change in study dosing (outside of any protocol-specified dose adjustments) or discontinuation from the study, significant additional concomitant drug treatment, or other therapy.• Exacerbation of a chronic or intermittent preexisting condition including either an increase in frequency and/or intensity of the condition.• New conditions detected or diagnosed after study intervention administration even though it may have been present before the start of the study.• Signs, symptoms, or the clinical sequelae of a suspected drug-drug interaction.• Signs, symptoms, or the clinical sequelae of a suspected overdose of either study intervention or a concomitant medication. Overdose per se will not be reported as an AE/SAE unless it is an intentional overdose taken with possible suicidal/self-harming intent. Such overdoses should be reported regardless of sequelae.

Events **NOT** Meeting the AE Definition

- Any clinically significant abnormal laboratory findings or other abnormal safety assessments which are associated with the underlying disease, unless judged by the investigator to be more severe than expected for the participant's condition.
- The disease/disorder being studied or expected progression, signs, or symptoms of the disease/disorder being studied, unless more severe than expected for the participant's condition.

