- If the investigator does not know whether or not the study intervention caused the event, then the event will be handled as “related to study intervention” for reporting purposes, as defined by the sponsor. In addition, if the investigator determines that an SAE is associated with study procedures, the investigator must record this causal relationship in the source documents and CRF, and report such an assessment in the dedicated section of the CT SAE Report Form and in accordance with the SAE reporting requirements.

Follow-up of AEs and SAEs

- The investigator is obligated to perform or arrange for the conduct of supplemental measurements and/or evaluations as medically indicated or as requested by the sponsor to elucidate the nature and/or causality of the AE or SAE as fully as possible. This may include additional laboratory tests or investigations, histopathological examinations, or consultation with other healthcare providers.
- New or updated information will be recorded in the originally completed CRF.
- The investigator will submit any updated SAE data to the sponsor within 24 hours of receipt of the information.

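### The TEAE rule in SAP 3.5.1 has no clause for worsening, so a screening-period AE that worsens on IP is missed unless the site enters it as a new event, which the documents do not require

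*SAP*

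**What the plan says.** SAP 3.5.1 calls an AE treatment-emergent "if the event started during the effective duration of treatment". It then gives the flag: "All events that start on or after the first dosing day and time/start time, if collected, but before the last dose plus" a lag time, whose length that section does not state. The last sentence closes off everything earlier: "The algorithm will not consider any events that started prior to the first dose date". The rule does not use severity, seriousness or change from the pre-dose state.

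The protocol starts AE collection early. Under Protocol 8.3.1 the active collection period "begins from the time the participant provides informed consent", and Protocol 4.1 describes participation as "including a screening period of up to 6 weeks".

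On how a worsening is recorded, the protocol points two ways. Protocol 10.3.1 lists among the events that are AEs: "Exacerbation of a chronic or intermittent preexisting condition including either an increase in frequency and/or intensity of the condition". Protocol 10.3.3, on follow-up of AEs and SAEs, says: "New or updated information will be recorded in the originally completed CRF".

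The incidence of treatment-emergent AEs is a named safety endpoint for both indications (Protocol 3.1, 3.2 and 9.4.3; SAP 3.2 and 3.5). Protocol 9.4.3 gives no TEAE definition of its own, so SAP 3.5.1 is the only operative one.

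**The concern.** A TEAE count is meant to show what appears or gets worse once treatment begins. A rule based only on start date captures the first and can lose the second. AEs with pre-dose start dates can be expected in this database, because collection begins at consent and screening can last six weeks. If one of them is mild before Day 1 and severe during treatment, the aggravation is the safety information of interest, and the stated algorithm can exclude it.

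The gap applies to any type of AE. Protocol 2.3.1 names nervous system and gastrointestinal effects as PDE4 class risks. A mild gastrointestinal complaint reported in screening that became severe on IP would be such a case.

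The error has one direction. Compared with a rule that includes worsening, this one can give an equal or lower count, never a higher one. It applies to both arms, so it reduces the between-arm difference only if IP aggravates more events than vehicle does. That is the situation a safety comparison exists to detect.

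**Working it through.** The plan states no figure to reproduce. The check applies the SAP 3.5.1 rule to each way a screening-period event can reach the database.

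1. **The event worsens on IP and the original entry is updated.** This follows the plain sense of Protocol 10.3.3. The start date stays before first dose, so the event is not flagged and the worsening is missed.
2. **The event worsens on IP and the worsening is entered as a new AE.** Protocol 10.3.1 allows this for an exacerbation of a chronic or intermittent condition. The new entry has an on-treatment start date and is flagged, so the worsening is counted.
3. **The event continues unchanged.** It is not flagged, which is correct.
4. **The event starts on Day 1 before dosing.** If times are collected, the start-time condition excludes it. The last sentence of 3.5.1 does not, since it refers only to earlier dates. If the event worsens later, it is handled as in case 1 or case 2.

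A condition known only from medical history, not recorded as an AE in screening, is not affected. Its exacerbation is the AE, and that begins on treatment. The gap is confined to events already recorded as AEs before first dose.

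Whether a worsening falls under case 1 or case 2 depends on site practice. No section of either document says that an increase in severity of an ongoing AE must open a new record. The follow-up sentence in Protocol 10.3.3 points towards case 1.

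**Size of one missed participant.** The inputs are the target numbers randomised per arm in Protocol Table 1: 28 for AD and 16 for psoriasis. The safety set is everyone randomised who applies at least one dose, so these are close to the largest denominators planned.

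- AD arm: 1/28 = 0.0357, or 3.6 percentage points.
- Psoriasis arm: 1/16 = 0.0625, or 6.3 percentage points.

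These are shifts in the row for a specific event term. The row for any TEAE moves by the same amount only if the participant has no other TEAE.

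**How many participants.** The documents give no rate for AEs ongoing at Day 1 or for their worsening. The number cannot be derived and may be zero.

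**The case against.** Several arguments limit the point, and most of them stand in part.

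- **Counted or not.** A reader might infer that a worsened screening AE can never be treatment-emergent. The documents do not support that, because an exacerbation entered as a new AE is flagged (case 2). The follow-up sentence in Protocol 10.3.3 also falls short of saying that a severity increase must stay on the original entry with its original start date. CRF completion instructions may settle this, but they are not among the documents. What remains is that the count depends on a recording choice that neither document fixes.
- **SAEs.** A reader might infer that an event becoming serious on IP would be hidden. SAP 3.5 lists SAEs and AEs leading to discontinuation in a separate item that is not limited to TEAEs. SAP 6.7 and 6.7.1 analyse serious AEs and withdrawals due to AEs alongside on-treatment AEs. Such an event should still appear there, even if it is absent from the TEAE tables.
- **Skin events.** A reader might expect the main loss to be in application-site reactions. A reaction to IP cannot begin before IP is applied, and local tolerability is assessed from Day 1 as its own endpoint. Expected signs of the disease under study are not AEs unless more severe than expected (Protocol 10.3.1). The skin is not the strongest ground for this point.
- **External standards.** SAP 3.5 says safety endpoints follow CDISC and sponsor standards, which may treat worsening as treatment-emergent. Their content is not in the documents. If they do include worsening, the explicit sentence in 3.5.1 conflicts with them. If they do not, the gap is real. The text needs editing in both cases.
- **Exploratory status.** SAP 6.7.1 describes safety analysis as generally exploratory, and no efficacy inference is affected. That limits the weight of the point. It does not justify a named endpoint whose value depends on how sites keep records.

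**Conclusion.** The point holds in limited form. SAP 3.5.1 states a start-date-only rule with an unqualified exclusion and no worsening clause. Followed as written, it can omit an AE aggravated on IP from the TEAE incidence. This is a rule that can give a wrong count, which is more than a missing detail.

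The loss is conditional: it occurs when the worsening is kept on the original entry and not entered as a new event. It falls mainly on nonserious AEs that become more severe without leading to discontinuation. Each affected participant is worth 3.6 points in an AD event row or 6.3 points in a psoriasis event row, assuming the full target arm size is dosed. The overall TEAE rate is affected only if the participant has no other TEAE. How often this will happen is unknown, and it may not happen at all. The change is still worth making before the analysis, because it is cheap and removes the dependence on site practice.

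**What to change.** In SAP 3.5.1, delete the sentence that excludes events starting before the first dose date. Define a TEAE as an event that either starts on or after first dose, or started before first dose and increases in severity or becomes serious on or after first dose, in both cases within the same window to last dose plus lag.

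Support this with one CRF completion instruction, tied to the follow-up text in Protocol 10.3.3. When an AE that began before first dose worsens afterwards, the site enters either a dated severity change or a new AE record with its own start date. Without a dated change the programmer cannot tell whether the worsening came before or after dosing.

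The cost is a short SAP edit, one site instruction and minor programming. It adds no visits, procedures or participants. TEAE counts may be slightly higher.

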#### **3.5.2. Laboratory Data**

The laboratory tests will be performed at time points identified in the Schedule of Activities. Unscheduled clinical labs may be obtained at any time during the study to assess any perceived safety concerns at the investigator's discretion.

#### **3.5.3. Vital Sign**

Vital signs (blood pressure, pulse, and oral or tympanic temperature) will be measured after a minimum of 5 minutes rest as indicated in the Schedule of Activities.

### 3.5.4. Electrocardiograms

Single 12-lead ECGs should be collected at times specified in the Schedule of Activities.

The baseline ECG values (the last measurement prior to receive study treatment on Day 1) will serve as each subject’s baseline values.

Only categorical summaries of the ECG data according to sponsor data standard will be provided.

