2.2.3. Preclinical Safety Data

In the pivotal 3-month toxicity studies in rats (oral) and minipigs (dermal), the systemic no-observed-adverse-effect levels (NOAEL) were identified as 4 mg/kg/day and 0.0104 mg/cm²/day (0.0052 mg/cm², BID), respectively, with systemic exposures of 2x and 1.2x, respectively, the projected maximum human exposure (uC_{av} = 9 pg/mL). The systemic NOAEL exposure identified in the more sensitive nonclinical species (minipig) was 11 pg/mL (C_{av}, unbound). The local (dermal) NOAEL was identified at the 0.03% concentration (BID) corresponding to 0.0052 mg/cm²/day (0.0026 mg/cm², BID) and represents an 17x multiple to the projected maximum human dermal dose of 0.0003 mg/cm²/day in the current study. Based on the completed nonclinical studies, local (skin) and systemic (cardiovascular, nervous, and gastrointestinal) target organs/systems were identified. Local reactions (erythema, edema) were observed in minipigs at ≥0.00174 mg/cm²/day (5.8x the highest planned clinical dermal dose, 0.0003 mg/cm²/day). A potential for skin sensitization by PF-07038124 was identified in a mouse local lymph node assay with a No Observed Effect Level (NOEL) of 0.015 mg/cm²/day (50x the highest planned clinical dermal dose, 0.0003 mg/cm²/day). Cardiovascular effects included increases in heart rate, contractility, and/or blood pressure in rats and/or dogs, and vascular

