9.4.3.1. Electrocardiogram Analyses

Changes from baseline for the ECG parameters QT interval, heart rate, QTc interval, PR interval, and QRS complex will be summarized by treatment and time.

The number (%) of participants with maximum postdose QTc values and maximum increases from baseline in the following categories will be tabulated by treatment:

Safety QTc Assessment

Degree of Prolongation	Mild (msec)	Moderate (msec)	Severe (msec)
Absolute value	>450-480	>480-500	>500
Increase from baseline		30-60	>60

In addition, the number of participants with uncorrected QT values >500 msec will be summarized.

CCI

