#### **6.7.4. Electrocardiograms**

Categorical summary tables will be summarized by treatment and time post-dose using sponsor reporting standards. Baseline is as defined in [Section 3.5.4](#). A listing of ECG comments on findings and normal/abnormal results will be provided.

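### The SAP limits ECG reporting to categories and drops the change-from-baseline summaries in Protocol 9.4.3.1 and SAP 3.5, so average shifts in QTc, PR and QRS would not be reported

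*SAP*

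**What the plan says.** Protocol 9.4.3.1 sets out two kinds of ECG output. The first is continuous: "Changes from baseline for the ECG parameters QT interval, heart rate, QTc interval, PR interval, and QRS complex will be summarized by treatment and time". A second kind is categorical and concerns QTc: the number of participants with "maximum postdose QTc values and maximum increases from baseline in the following categories will be tabulated by treatment". Those categories are absolute values of >450-480, >480-500 and >500 msec, and increases of 30-60 msec (headed Moderate) and >60 msec (headed Severe). A count of uncorrected QT above 500 msec is added.

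SAP 3.5 keeps both ideas in its list of safety endpoints: "Incidence of clinical abnormalities and change from baseline in selected clinical laboratory values, ECG measurements, and vital signs".

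SAP 3.5.4 defines the ECG baseline as the last measurement before treatment on Day 1 and then states: "Only categorical summaries of the ECG data according to sponsor data standard will be provided". SAP 6.7.4 follows that rule: "Categorical summary tables will be summarized by treatment and time post-dose using sponsor reporting standards". Its only other output is a listing: "A listing of ECG comments on findings and normal/abnormal results will be provided". Neither SAP section states any cut-points.

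**The concern.** SAP 3.5.4 is an explicit exclusion. It is not a silence that a sponsor standard would fill. A programmer working from SAP 3.5.4 and 6.7.4 would produce no mean or median change for any ECG parameter, although the protocol asks for this by treatment and time and SAP 3.5 names it.

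The protocol describes this as the first study of the ointment in participants with AD or psoriasis, and its nonclinical section reports: "Cardiovascular effects included increases in heart rate, contractility, and/or blood pressure in rats and/or dogs, and vascular" injury. A reader of the study report would expect to see whether ECG intervals moved on average. In arms this small, a category table says little about a modest average shift. For PR and QRS, neither document's analysis text gives any category at all.

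**Working it through.** **Comparison of the texts.** There is no stated figure to reproduce, so the check is what remains for each parameter if SAP 3.5.4 and 6.7.4 are followed.

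| Parameter | Protocol 9.4.3.1 | What remains under the SAP |
|---|---|---|
| QTc | Change by treatment and time; absolute and increase categories | Categories (cut-points not stated in the SAP); no average change |
| QT | Change by treatment and time; count >500 msec | Categorical only; no average change |
| PR, QRS | Change by treatment and time | Normal/abnormal listing; no visible category; no average change |
| Heart rate | Change by treatment and time | No ECG average, but pulse is a vital sign (SAP 3.5.3), summarized at baseline and Weeks 2, 4 and 6 (SAP 6.7.3), with change from baseline in Protocol 9.4.3 |

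Protocol Appendix 7 does name PR above 280 msec and new bundle branch block with QRS above 120 msec, but as findings that may be adverse events. They are not analysis categories.

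**Numbers available.** In both Schedules of Activities the ECG is taken at screening, Day 1 and Week 6, and not at early termination. Week 6 is therefore the only scheduled post-baseline ECG. The relevant counts are the planned completers, 21 per arm in AD and 12 per arm in psoriasis (Protocol Table 1). The randomized counts of 28 and 16 would overstate the information.

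**Illustration: precision of a mean difference.** The SD of QTcF change is in neither document. I assume 15 msec and show 10-20 msec. The level is 90%, as the SAP uses for its efficacy intervals.

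Half-width = t(0.95; 2n-2) x SD x sqrt(2/n)

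- AD, n = 21, 40 df: 1.684 x 15 x sqrt(2/21) = 1.684 x 15 x 0.3086 = 7.8 msec. For SD 10 and 20: 5.2 and 10.4 msec.
- Psoriasis, n = 12, 22 df: 1.717 x 15 x sqrt(2/12) = 1.717 x 15 x 0.4082 = 10.5 msec. For SD 10 and 20: 7.0 and 14.0 msec.

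**Illustration: what the 30 msec category would show.** Assume normal changes with mean zero on vehicle and a true average shift of 10 msec on active.

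P(increase of at least 30 msec) = 1 - Phi((30 - shift)/SD)

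| SD (msec) | Vehicle | Active | Expected of 21 (AD), vehicle v active | Expected of 12 (psoriasis), vehicle v active |
|---|---|---|---|---|
| 10 | 0.0013 | 0.0228 | 0.0 v 0.5 | 0.0 v 0.3 |
| 15 | 0.0228 | 0.0912 | 0.5 v 1.9 | 0.3 v 1.1 |
| 20 | 0.0668 | 0.1587 | 1.4 v 3.3 | 0.8 v 1.9 |

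Each expected count is the probability times the number of completers; for example, 0.0912 x 21 = 1.9. An average shift of 10 msec would thus add at most about two participants per arm to the category, which cannot be told from chance.

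**The case against.** **The SAP is allowed to do this.** Protocol section 9 and SAP section 2 let the SAP modify the protocol, and a protocol amendment is called for only with major changes to the primary endpoints or their analysis. A reader might infer a breach of the protocol, and the documents do not support that. The permission supplies no reason for the change, however, and it does not settle the disagreement within the SAP.

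**SAP 3.5 is a general list.** Its wording, "change from baseline in selected clinical laboratory values, ECG measurements, and vital signs", could be met by tabulating QTc increases from baseline by category, and the secondary endpoint in Protocol 3.1 and 3.2 is the incidence of clinically significant ECG changes. SAP 3.5.4 would then be the specific rule. This softens the internal conflict for QTc. It does not help PR or QRS, for which no category is visible.

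**The loss is narrower than it looks.** A reader might infer that moderate heart-rate or QTc shifts would go unseen. The documents do not support that. The protocol's own Moderate category counts individual QTc increases of 30-60 msec. It is likely to be used, although the SAP cites only the sponsor standard and does not restate it. Pulse is summarized at three post-baseline visits, more often than the ECG. The nonclinical findings quoted concern heart rate, contractility and blood pressure, and vital signs cover the first and last of these. The visible text reports no nonclinical QT signal. Participant-level QTcF rules in Protocol 7.1 and 8.2.4 do not depend on these tables.

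**A between-arm interval goes further than the protocol.** This stands. The protocol asks for summaries, and SAP 6.7.1 treats safety analysis as generally exploratory. In psoriasis the interval would also be wide: at SD 15, an observed difference of 10 msec would not exclude zero.

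**Conclusion.** The point holds in limited form. The SAP removes, without a visible reason, a continuous ECG summary that the protocol specifies and that its own endpoint list names. What is lost is the reporting of average shifts in QTc, PR and QRS, including QTc shifts too small to carry individuals past 30 msec.

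Two limits apply. That individual QTc increases of 30 msec or more remain visible depends on the protocol's categories being the ones used. All msec figures for precision and expected counts rest on the assumed SD of 10-20 msec; they only illustrate the size, and the textual finding does not depend on them. Severity is minor: no design, sample size or efficacy conclusion is affected.

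**What to change.** In SAP 3.5.4 and 6.7.4, replace the restriction to categories with two items:

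1. The QTc categories of Protocol 9.4.3.1, written out in the SAP, with the count of uncorrected QT above 500 msec.
2. Descriptive change from baseline to Week 6 in heart rate, PR, QRS, QT and QTcF, by arm and by indication.

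A between-arm difference with a 90% CI is optional. If the sponsor prefers categories alone, SAP 3.5 should drop change from baseline in ECG measurements, and the SAP should give the reason for departing from Protocol 9.4.3.1.

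The cost is one standard table. The ECGs are already scheduled and the baseline is already defined, so there is no new data collection.
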